Patients will receive treatment until progressive disease based on "RECIST v1.1-GIST-specific Criteria", intolerable adverse events or withdrawal of consent. If progressive disease is confirmed by the independent radiologic review using "RECIST v1.1-GIST-specific Criteria", patients who receive DCC-2618 or sunitinib will discontinue treatment with the study drug.

Table 1: Schedule of Assessments

Evaluation/Procedure ¹	Screening 2		Cycle 1		Сус	le 2	≥ Cycle 3	EOT visit	Safety follow- up	Overall survival
Cycle Day	-28 to -1	1 (Baseline)	15 (± 1 day)	29 (± 1 day)	1 (± 3 day)	29 (± 3 day)	1 (± 3 day)	(Within 7 days after the last dose)	Within 30 days after the last dose (± 5 day)	follow-up ³ (Every 2 month \pm 10 days)
Come to the Study Site	X	X	X	X	X	X	X	X		
Tel									X	X
Informed consent	X									
Inclusion/Exclusion criteria	X									
Previous medical history and tumor history	X									
Previous medications/treatment ⁴	X									
Pregnancy test ⁵	X	X*			X		X	X		
Hepatitis B/C tests ⁶	X						X	X		
HIV antibody test	X									
Clinical laboratory tests										
Blood routine	X	X*	X	X	X	X	X	X		
Blood biochemistry	X	X*	X	X	X	X	X	X		
Blood coagulation function ⁷	X	X*	X	X	X	X	X	X		
Urine routine ⁸	X	X*			X		X	X		
TSH, FT3 and FT4 ⁹	X	X*					X	X		
Physical examination	X	Examination will be arranged based on clinical findings and/or patients' chief complaints								
ECOG PS ¹⁰	X	X*	X	X	X	X	X	X		
Vital signs and weight ¹¹	X	X*	X	X	X	X	X	X		
Height	X									
12-lead ECG ¹²	X	X*			X		X	X		
Echocardiography/13	X						X	X		
Dermatologic examination ¹⁴	X						X	X		

Evaluation/Procedure ¹	Screening 2		Cycle 1		Cyc	le 2	≥ Cycle 3	EOT visit	Safety follow- up	Overall survival
Cycle Day	-28 to -1	1 (Baseline)	15 (± 1 day)	29 (± 1 day)	1 (± 3 day)	29 (± 3 day)	1 (± 3 day)	(Within 7 days after the last dose)	Within 30 days after the last dose (± 5 day)	follow-up³ (Every 2 month ± 10 days)
AEs reporting			Co	ntinuing from	m signing an l	CF to the saf	fety follow-up			
Concomitant medicines/other treatment				From t	he first dose o	f the study d	rug to safety follo	ow-up		
Administration of study drug ¹⁵		X	X	X	X	X	X			
Distribution and reconciliation of the study drug		X			X		X			
PK sampling ¹⁶		X	X		X		X			
Molecular test report, marking KIT/PDGFRA mutation status ¹⁷	X									
Archived tumor tissue sample/tumor biopsy ¹⁸	X									
Optional tumor biopsy 19								X		
Imageological examination ²⁰	X				X		X			
PD sampling (plasma) ²¹		X						X		

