Validation of progressive disease: if the independent radiologic review considers there is no progressive disease based on "RECIST v1.1-GIST-specific Criteria", the patient will continue receiving the study drug, unless the study drug should be discontinued for medical need (that is, fast progression or clinical worsening). If investigators confirm progression according to clinical worsening, radiographic images should be performed and reviewed by independent radiologic institutions to confirm whether the patient has progression. The basis of confirming progression according to clinical worsening must be recorded in source data and electronic case report form of patients. If the investigator confirms progressive disease according to "RECIST v1.1-GIST-specific Criteria", the investigator should wait for confirmation by the independent radiologic review and then terminate the patient's treatment. If the investigator doesn't hope to confirm by the independent radiologic review or hopes to terminate the patient's treatment according to progressive disease based on "RECIST v1.1-GIST-specific Criteria" before obtaining results of the independent radiologic review, it is necessary to discuss with the sponsor. Radiographic examination of patients of various treatment groups should be performed according to the predetermined time and cycle will not be influenced by suspension or delay of treatment with the study drug. If the patient discontinues treatment for reasons other than progressive disease, death, withdrawal of consent and lost to follow-up, the patient should receive radiographic examination for tumor assessment according to the specified time interval after treatment withdrawal until progressive disease based on "RECIST v1.1-GIST-specific Criteria" or initiation of new anti-tumor therapy.

- Blood samples of patients who use DCC-2618 (ripretinib, ZL-2307) and sunitinib will be collected within 60 minutes prior to administration on C1D1 (baseline), and when the independent radiologic review confirms progressive disease according to "RECIST v1.1-GIST-specific Criteria" or at EOT visit.
- 22. Randomization can be carried out on Day -1. Patients who will be randomized on C1D1 can be randomized on the former Friday.

.

LIST OF ABBREVIATIONS

List of Abbreviations	Definition
AE	AEs
AESI	Adverse events of special interest
ALT	Alanine aminotransferase
AML	Acute myeloid leukaemia
ANC	Absolute neutrophil count
ASM	Aggressive systemic mastocytosis

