1.3.2.2. Clinical Pharmacokinetics and Pharmacodynamics Markers

In the non-clinical study, it has been confirmed that DP-5439 is an active metabolite of DCC-2618 (ripretinib, ZL-2307) and its activity features are similar to DCC-2618.

Plasma $T_{1/2}$ of metabolite is longer (30 - 60 hours), indicating QD dosing schedule is feasible. Sub-study of food influence revealed that DCC-2618 (ripretinib, ZL-2307) taken with diet didn't have negative influence on absorption. Please refer to Section 1.5.2 for more information of basis of current study dose, dosing schedule and treatment duration.

In GIST paitents who have previously received multiple therapies, DCC-2618 (ripretinib, ZL-2307) could rapidly eliminate extensive KIT mutation in plasma DNA. In general, on Day 15 of Cycle 1, total plasma concentration (C_{max}) at the start dose of 100 mg BID was very high, more than 5 am (3,000 ng/mL); the observed mean exposure was far more than the target plasma level, including exposure level for KIT mutations (V654A and T670I) most insensitive to inhibiting DCC-2618 (Ripretinib, ZL-2307).

In the phase 1 study, next-generation plasma cell-free DNA (cfDNA) sequencing was carried out in GIST patients at baseline, Week 2, during patients' participation in the study and at the end of study (Figure 3). Mutations were tested and quantified with Guardant 360 v2.9 or v2.10. According to preliminary data (cut-off 18 April 2018), circulation tumor DNA (ctDNA) was tested in most baseline cfDNA. In 131 GIST patients with KIT mutation, KIT mutation was detected in baseline ctDNA test of 95 patients and the mutation range covered exons 9, 11, 13, 14, 17 and 18 (Figure 3). Of 9 enrolled patients with PDGFRA exon 18 mutation, PDGFRA exon 18 mutation was only detected in ctDNA samples of 2 patients (if archived tissues are available, it will be confirmed by testing the tissues).

Figure 3: KIT mutation in baseline ctDNA of 131 GIST patients listed according to treatment line (n = 95)

Each list represents one GIST patient. Each color bar in each line represents one or multiple mutations detected in KIT exons 9, 11, 13, 14, 17 and 18. In patients with KIT exon 9/11 mutations detected in baseline ctDNA, secondary mutation occurred in KIT exons 13, 14, 17 and 18 of second- to ≥ fourth-line patients

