2.3. Exploratory objectives

- To evaluate potential biomarkers in blood or tumor tissue which might predict response to DCC-2618 (ripretinib, ZL-2307)
 - To understand potential drug resistance mechanism to DCC-2618 (ripretinib, ZL-2307) in GIST.
 - To characterize KIT and PDGFRA mutations at baseline and DCC-2618 (ripretinib, ZL-2307)-driven longitudinal mutant allele frequency changes in plasma.

Note: Blood samples and tumor tissues for exploratory purpose will be collected after obtaining the approval of China Human Genetic Resources Administration Office.

3. Study Design

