9.2.3. Exploratory endpoint

- KIT/PDGFRA mutation of tumor tissues at baseline and specific time points (e.g., resection of metastasis or progressive disease during the study).
- KIT/PDGFRA mutations and mutant allele frequency at baseline and the treatment effect of DCC-2618 (ripretinib, ZL-2307) on KIT/PDGFRA mutant allele frequency (MAF).

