9.5.8. Biomarkers and pharmacodynamics analysis

Observe baseline KIT and PDGFRA mutation in plasma and features of mutation allele frequency change during the study

The Mann-Whitney U test will be used to analyze statistical difference between treatment groups in terms of treatment effectof DCC-2618 (ripretinib, ZL-2307) and sunitinib on mutation frequency tested using ctDNA at all time points. Formal hypothesis test will not be performed.

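### Plasma ctDNA is drawn only before the first dose and at progression or end of treatment, so early suppression, nadir and time course of mutant allele frequency under drug cannot be assessed

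*Combined protocol and SAP*

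**What the plan says.** In Table 1 the plasma pharmacodynamic row is marked only under C1D1 and the EOT visit. Note 21 covers both arms: samples are "collected within 60 minutes prior to administration on C1D1 (baseline), and when the independent radiologic review confirms progressive disease" under the GIST-specific criteria, "or at EOT visit". Section 6.13.2.2 refers back to Table 1 for blood samples, speaks of longitudinal change in ctDNA frequency, and adds no time point.

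Three other places state what these samples are for:
- Section 2.3 (exploratory objectives) asks for "ripretinib, ZL-2307)-driven longitudinal mutant allele frequency changes in plasma".
- Section 9.2.3 lists the effect of ripretinib treatment on KIT/PDGFRA MAF as an exploratory endpoint.
- Section 9.5.8 plans a Mann-Whitney U comparison of the two arms "on mutation frequency tested using ctDNA at all time points", then says that no formal hypothesis test will be performed.

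**The concern.** The stated aims need measurements while the drug is acting, and the schedule supplies none. A patient whose MAF falls early and returns by progression would show little or no change between the two samples. The protocol's introduction makes this plausible: it attributes progression after targeted treatment mainly to secondary KIT mutations.

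The between-arm comparison has a further problem. At baseline the randomised arms should not differ. The second sample is taken when the patient progresses or stops, so its timing depends on outcome and is expected to differ by arm. A difference at that point mixes drug effect with when and why patients stopped.

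The phase 1 schedule in Section 1.3.2.2 shows what is absent here. There, plasma "sequencing was carried out in GIST patients at baseline, Week 2", during participation and at the end of study. Samples not drawn during treatment cannot be recovered later.

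**Working it through.** **Schedule.** Under Table 1 and note 21, the number of scheduled ctDNA samples between C1D1 and progression or EOT is 0. Counting from the first dose, the visits that pass without a plasma ctDNA draw are:
- by 6 months (planned sunitinib median): C1D15, C1D29, C2D1, C2D29, C3D1, C4D1, C5D1, which is 7 visits;
- by 9 months (planned ripretinib median): the same plus C6D1 and C7D1, which is 9 visits.

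Pharmacokinetic blood is taken at C1D15, C2D1 and C3D1, but only in the ripretinib arm and for drug concentration. Blood routine and biochemistry are scheduled at C1D15 in both arms.

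**Inputs for the missing second sample** (Section 9.1): median PFS 9 and 6 months; 49 patients per arm; 7 months' enrolment plus 7 months' follow-up; 5% annual drop-out; 58 PFS events at the primary analysis. Section 3.3 allows the study to run to 20 months after enrolment ends. Exponential PFS and uniform accrual are my assumptions.

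**The plan's own figure first.** Let λ = ln 2 / median, g = −ln(0.95)/12 and t = λ + g. With accrual R = 7 and minimum follow-up F = 7, the share still event-free and under follow-up is S = [exp(−tF) − exp(−t(F+R))]/(tR). Expected events are 49 × (λ/t) × (1 − S):
- ripretinib 26.4, sunitinib 33.4, total 59.8 against 58 stated, within about 3%;
- still event-free and under follow-up: 21.2 of 49 (43%) and 14.3 of 49 (29%).

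**Event-free patients without drop-out** (g = 0, so t = λ; λ = 0.0770 for ripretinib and 0.1155 for sunitinib):

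| Cutoff | Ripretinib | Sunitinib | Total |
|---|---|---|---|
| 14 months from first enrolment (F = 7) | 49 × (0.583 − 0.340)/0.539 = 22.1 | 49 × (0.445 − 0.198)/0.809 = 15.0 | 37 of 98 |
| 20 months after enrolment ends (F = 20) | 49 × (0.214 − 0.125)/0.539 = 8.1 | 49 × (0.099 − 0.044)/0.809 = 3.3 | about 11 of 98 (12%) |

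These count patients without a PFS event. Those who stopped for another reason may have an EOT sample, and a patient who died may have none, so the figures approximate the number lacking a second sample.

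**The case against.** Much can be said for the plan as it stands. The endpoint is exploratory, Section 9.5.8 disclaims formal testing, and neither the primary PFS analysis nor the consistency criterion uses MAF. All of that stands and limits the weight of the point. It does not remove it, because an informal comparison of arms at outcome-dependent times is confounded in the same way as a formal one.

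Three stronger readings are tempting, and the documents do not support them:
- *The MAF objective cannot be answered at all.* A paired change from baseline to progression or EOT exists for patients with both samples, and it serves the resistance-mechanism objective in Section 2.3.
- *All second samples are taken at failure and will be pooled.* Section 8.1 lists other reasons for stopping, including adverse events and patient request. The main reason is recorded, and 9.5.8 does not say that the samples are pooled.
- *A planned link to the phase 1 finding of rapid plasma clearance is lost, or 41% of patients will lack a second sample.* The only bridge planned is to INTRIGUE, judged on the PFS hazard ratio. The 41% is (98 − 58)/98 = 40/98. It applies only at the 58-event cutoff, to which no section ties the MAF analysis. It also differs from the modelled 37, because the no-drop-out model gives about 61 events by 14 months.

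**Conclusion.** The point holds in limited form. The two-sample schedule can describe mutations and MAF before treatment and at progression or EOT. It cannot show early suppression, nadir or time course under drug, and it gives no sound basis for a between-arm treatment effect on MAF. Followed as written, Section 9.5.8 could misstate the drug effect.

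The finding about the schedule needs no modelling. How many patients lack a second sample depends on the analysis date: about 22 and 15 of 49 (ripretinib and sunitinib) are event-free at 14 months, and about 8 and 3 if the analysis waits until 20 months after enrolment ends. Waiting reduces the missing samples and their imbalance, but the timing of the second sample still depends on outcome. The change should be made, but it does not bear on the trial's primary conclusion.

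**What to change.** Preferred: add one ctDNA tube in both arms at the C1D15 blood draw already scheduled, when both arms are on drug. In Section 9.5.8, make change from baseline to C1D15 the measure of treatment effect on MAF, and update Table 1, note 21 and Section 6.13.2.2 to match. C2D1 should not be used for the between-arm comparison: it follows the 2-week sunitinib break, whereas ripretinib is given continuously, so drug effect would be mixed with time off treatment. The cost is one tube and one assay per patient, and possibly an update to the human genetic resources approval mentioned in Section 2.3. No extra venepuncture is needed.

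If no tube is added, the change is text only:
- Restate Sections 2.3, 6.13.2.2 and 9.2.3 as mutations and MAF at baseline and at progression or EOT.
- Remove the treatment-effect wording from 9.2.3 and 9.5.8, and the between-arm Mann-Whitney test from 9.5.8.
- Describe the samples by arm, with progression samples shown separately from other EOT samples.

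Keeping the between-arm test but restricting it to progression samples would not help, because it would still condition on an outcome that follows randomisation. The text-only route costs nothing in samples but gives up any statement on the drug's effect on MAF during treatment.

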1.1. Introduction

Studies revealed that activating mutation of KIT or PDGFRA of receptor tyrosine kinase exists in many cancers such as gastrointestinal stromal tumor (GIST), melanoma subtype, seminoma of testis and acute myeloid leukemia (AML) as well as myeloproliferative neoplasm such as systemic mastocytosis (SM) including aggressive systemic mastocytosis (ASM) and mast cell leukemia^[1,2,3,4,5]. Studies also revealed that GIST, melanoma, AML, glioma and neuroendocrine tumor presented abnormal wild-type KIT and/or PDGFRA overexpression[6,7,8,9].

Zai Lab

Most GIST is induced by activated mutation in KIT (about 80%) or relevant PDGFRA (about 10%) receptor tyrosine kinase^[11,300]. In GIST patients, exon 9 or 11 mutations are the most common in KIT mutation. Primary exon 11 mutation destroys autoinhibitory domains of kinase and primary exon 9 mutation increases receptor dimerization. Both mechanisms lead to ligandindependent receptor activation, making the growth and transformation of cells out of control. Multiple KIT target treatments have been approved for the treatment of GIST, but the efficacy is limited.

[figure not shown]
After receiving target treatment, secondary drug-resistant KIT mutation generally occurs in the catalytic domain of kinase and these mutations are usually reflected in embedded conformational switch control mechanism that regulates KIT activity (

Zai Lab

Figure 2) Secondary KIT mutations usually occur in exons 13 and 14 (approaching adenosine triphosphatase [ATP]-binding pocket), and destroy drug binding capacity in space or activate KIT conformation. These mutations can also occur in the activation loop (conformational control switch) encoded by exons 17 and $18^{[10,11]}$. Activation loop mutation can transform kinase into activation conformation, making it difficult to bind to the approved therapeutic drugs^[12]. Other diseases harboring primary KIT (or PDGFRA) activation loop mutations include SM, AML and PDGFRA-induced GIST^[6,13,14].

Figure 2: Various secondary KIT mutations in cross-exon 13 - 18 in GIST patients

Distribution of secondary KIT mutation

Source: Liegl B, Kepten I, Le C, Zhu M, Demetri GD, Heinrich MC, et al. Heterogeneity of kinase inhibitor resistance mechanisms in GIST, J. Pathol. 2008 Sep;216(1):64-74.

Imatinib is the first KIT inhibitor and was approved in 2002 for the treatment of advanced GIST ^[15]. Imatinib generally cannot cure unresectable and/or metastatic diseases and its complete response rate (CR) was about 5% and objective response rate (ORR) was 68% ^[16]. Over 80% of GIST patients obtained clinical benefit from imatinib monotherapy. However, imatinib resistance was basically unavoidable for patients and over half of patients had progressive disease within 2 years ^[17]. The main cause for progression was secondary KIT kinase mutation, inducing resistance to imatinib ^[11]. Although imatinib can effectively inhibit exon 11 mutation in KIT and dose increase to 800 mg was effective to exon 9 mutation, imatinib doesn't or almost doesn't have inhibitory effect on KIT and PDGFRA mutation, especially on mutations of conformation dynamic mediating switch activation ^[17], ^{18]}.

In 2006, sunitinib was approved as second-line therapy in GIST patients who have progressed after imatinib treatment or are intolerant to imatinib. Sunitinib has a stronger inhibitory effect on exon 9 mutation than imatinib and a weaker inhibitory effect on exon 11 mutation [14, 17]. In addition, sunitinib presented anti-tumor activity to KIT exons 13 and 14 mutations, but only half of the patients benefited from it, with a median progression-free survival (PFS) of 5.5 months^[17]. Sunitinib was ineffective in patients with KIT exons 17/18 mutations and PDGFRA exon 18 mutation r in the activation loop.

Regorafenib was approved as third-line therapy in 2013 in adult patients with metastatic and/or unresectable GIST who have progressed after receiving imatinib and sunitinib treatment or are not tolerant to imatinib and sunitinib. Besides inhibitory activity to KIT exon 11 mutation, regorafenib is the only approved therapy with an inhibitory activity to KIT exon 17 mutation subtype. For patients responding to regorafenib, PFS was nearly 5 months. Regorafenib cannot effectively treat some patient with KIT mutation. In such case, these patients may have other

or multiple secondary mutations, leading to resistance to regorafenib [11]. Studies showed that for an individual patient, tumor heterogeneity and multiple secondary KIT mutations were observed in different regions of a tumor or different metastatic sites [11].

Complex heterogeneity of KIT mutation in individual patient is a main cause for drug resistance ^[11]. Kinase inhibitor that can extensively inhibit clinical KIT mutation or multiple KIT mutation in individual GIST patients has a high treatment value for refractory GIST patients. What's more, it is an important treatment objective to confirm whether DCC-2618(Ripretinib, ZL-2307) can delay the occurrence of KIT mutations leading to drug resistance.

At present, no kinase inhibitor that can extensively inhibit secondary drug-resistant mutation in GIST patients has been marketed. Therefore, it is urgent to develop kinase inhibitor that can effectively inhibit multiple KIT and PDGFRA mutations.

1.2. Clinical Indications

DCC-2618 (ripretinib, ZL-2307) is a KIT and PDGFRA kinase inhibitor. At present, the drug is under development and expected to treat GIST and other advanced malignant tumors induced by proto-oncogene tyrosine protein kinase. DCC-2618 can not only inhibit KIT and PDGFRA but also inhibit CSF1R (FMS), VEGFR2 and TIE2. According to literatures, these substances seldom induce tumor progression, but are associated with tumor growth.

GIST is the most common type of sarcoma, formed in human mesenchymal cells but is a relatively rare cancer subtype [19]. There are approximately 3000 - 6000 new GIST patients every year in America [20, 21, 22] and the age of onset is usually 50 - 70 years, with a similar prevalence in males and females [23]. Surgery, as the main treatment for local GIST, can realize a radical effect, but over half of patients had local and/or distant metastasis [24]. Approximately half of patients had metastatic or unresectable GIST, while radiotherapy and traditional chemotherapy are ineffective in these patients [19, 24]. In the era of targeted cancer therapy, several new effective therapies have been developed for metastatic and recurrent GIST though CR is seldom reached [19]. Most patients have resistance to treatment within several months to years depending on treatment method [20], which is similar to result observed in targeted therapy of other tumors.

1.3. DCC-2618 (Ripretinib, ZL-2307)

DCC-2618 (Ripretinib, ZL-2307) is a new orally administered KIT kinase and PDGFRA kinase inhibitor developed by Deciphera Pharmaceuticals, LLC (thereafter refer to "the Sponsor") using its special kinase switch control inhibitor technological platform. DCC-2618 (Ripretinib, ZL-2307) can comprehensively and potently inhibit extensive primary and secondary KIT and PDGFRA kinase mutants, including primary KIT exons 9 and 11 mutations, secondary exons 13 and 14 mutations in KIT ATP-binding/transformation pocket, and primary and secondary exons 17 and 18 mutations in activation loop conformation-control switch region. DCC-2618

(Ripretinib, ZL-2307) can also inhibit primary exon 18 D842V mutations in PDGFRA conformation-control switch region and assist in inhibiting exon 12 mutation in switch region. DCC-2618 (Ripretinib, ZL-2307), as an enhanced type II kinase inhibitor, penetrates embedded KIT/PDGFRA switch pocket by binding to extensively inhibit KIT/PDGFRA mutants.

